## **Study Design/Procedures**

**Directions: 1) Describe the overall study design. 2) Provide a description of all study-related research procedures being performed, including the length of time involved. 3) Include procedures being performed to monitor research participants for safety or minimize risks. 4) Describe the source records including medical or educational records, which will be used to collect data about subjects.**

*The study is a four-year randomized controlled trial in Northeastern Ohio and includes a convenience sample of family caregivers of adults with bipolar disorder. After eligibility is verified during phone screening by team member, the consent forms will be reviewed verbally, questions about the study will be answered, and the study enrollment/first data collection appointment will be made.*

*There are three structured data collection time points (T1/enrollment, T2/ 6months after initiation of intervention, T3/ 12 months after initiation of intervention); these will be face-to-face with a research assistant, using a desktop, laptop, or iPad with secure REDCap software. During the enrollment and first data collection meeting, we will obtain informed consent from the caregiver. Caregivers will have time to ask questions about the study and review the consent form before signing it.*

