**COVID-19 Modifications:** Some T2 and T3 data collection will take place remotely, as a response to the COVID-19 pandemic (beginning in April 2020). We will use phone (Google voice) or Zoom (computer video) to complete the data collection. An email will be sent, if possible, to participants with the answer response choices for each survey. If we are using phone for data collection, the Research Assistant (RA) will ask the participant each question and record the responses in our REDCap Surveys project. If collecting data using Zoom video, the RA will share the screen of the REDCap Surveys project, and record the answers for the participant as they review each survey question. If neither of those two options are available for the participant (e.g., limited phone minutes, inability to use Zoom), the study may email the REDCap surveys to study participants for them to complete on their own at an agreed upon date / time (similar to in-person appointment); in this instance, the RA can be available to answer questions or clarify information as needed, by phone or email. It may be that none of these options will work for a study participant, in which case we will consider that data "missed" if we cannot wait to collect the data in person at a later date (when we resume normal study activities). The precise method(s) will depend on the ability and resources of the study participant. For these data collection sessions, HRV data (collected by placing electrodes on the wrists) may not be collected and will be considered missing data (see following page for more detail regarding remote HRV data collection). We will contact active participants with Zoom/ phone instructions, by phone/text and/or email, as needed, and we will record the methods used

for each data collection done remotely. A COVID-19 questionnaire will be asked at remaining T2 and T3 data collections; script to obtain consent for these questions is included in the questionnaire.

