*Individuals will be encouraged to continue with the interventions if they found them helpful (for BF, caregivers will have been given information on deep-breathing techniques without using a device). Caregivers who cannot be reached by phone or email for follow-up (either intervention or data collection) will have a letter sent to them if they have consented to having a letter sent to their home. Occasionally, calls will need to be made to study participants outside of the office (e.g., evenings/ weekends; when a research team member is working remotely/ in the field) or participants will request to be contacted by text. In these instances, the research team will use Google Voice, which allows users (research team) to set up a phone number through their CWRU email and is connected to their personal mobile phones. Calls and texts can be made to/ from the mobile phones while masking the actual phone number. When the research team is not working, calls will be directed to voicemail.*

*From Modification #8 (approved 03/06/2019)-- At the end of the T3 data collection, study participants will receive a brochure from each of the three interventions being researched, as well as an answer sheet for Caregiver Knowledge of Bipolar Disorder Questionnaire. Study participants who received an intervention will be asked a series of questions (up to 16) about their experience with, and opinion of, the intervention they received. Study participants who have already completed all three data collection sessions and have already agreed to be contacted for any questionnaire follow-up will be called and asked questions over the phone.*

Page 14 of 29

*The supplemental analysis will use baseline data (T1) to explore relationships among caregiver characteristics (race and gender), psychological stress (caregiver reactions and caregiving involvement), and physiological stress (heart rate variability time and frequency domains). De-identified baseline data from the demographic measures, psychosocial measures (caregiver reactions, caregiver involvement) and the HRV measurements will be used for this analysis.*

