## **Data Analysis Plan**

**Directions: Describe the data analysis plan, including any statistical procedures. If applicable, provide a power analysis, and study/safety endpoints.**

*The primary aim (A1) is to examine differences across four groups of family caregivers on caregiver health over time. The underlying analyses for A1 are built around the repeated measures analysis of variance (RMANOVA). The primary analysis will be a set of 4 group X 3 time waves RMANOVA. These analyses will compare the four groups: 1) a control group (no intervention); 2) education (usual care); 3) SM-need; or 4) SM-preference across three time waves of health risks and physical and mental health outcomes. When using RMANOVA, one not only assesses mean differences across time, but also assesses group differences and the interaction of time X group, which allow us to test the trend of the means over time across the four groups.*

*The RMANOVA, not only can be used to determine if there are mean differences across the three time periods, it can utilize orthogonal polynomial contrasts to determine if there are mean and quadratic trends of the means across time. Orthogonal polynomials are weights assigned to each time period that model a linear or quadratic non-linear trend. RMANOVA can determine if these trends in the mean are significant. A linear trend is indicated if there is a change in direction based on scores across the time waves. The major assumption to be tested with RMANOVA is sphericity. Sphericity is a form of compound symmetry and refers to the equality of variances of the differences between time waves. If the assumption of sphericity is violated based on the Mauchly's test, SPSS provides and adjusted F, df, and P-value in RMANOVA to account for the violation.*

*Secondary aims are to: A2) explore whether caregiver need or their preference for interventions associated with: a) care recipient's symptoms; b) caregiver reactions; and c)*

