## **Withdrawal of Research Participants**

**Directions: Describe the anticipated circumstances under which research participants will be withdrawn from the research without their consent. Also include the procedures that will be followed when a research participant withdraws or are withdrawn from the research, including partial withdrawal from procedures with continued data collection.**

N/A

*Participants have the option of withdrawing from the study at any time and can request that no further information be shared about them from that point on. If a study participant withdraws consent to participate in the study, a research team member will notify the project manager to complete end of study documentation.*

*The project manager will review cases regularly with research staff to determine which study participants should be withdrawn from the study. Research participants will be withdrawn from the research without their consent if they are non-responsive to phone calls, emails, texts, or letters and considered lost to follow up.*

*Data that were collected prior to a study participant's withdrawal will be de-identified and still be used in the data analysis for the study. After withdrawal, no further data will be collected for that participant.*

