*The SMC will review 1) all causes of mortality (e.g., caregiver death); 2) issues with participation (e.g., numbers and reasons for withdrawing from the study or refusing interventions, etc.) as well as recruitment refusal (percent and reasons) and subject attrition (percent and reasons); 3) missing data (including whether there are systematic patterns or whether data are missing at random); and 4) errors in data entry (which are expected to be minimal given the use of software for data collection with direct download into SPSS). In addition, differential attrition from the intervention groups (including the control and usual care groups, and the groups assigned to intervention based on need or personal preferences) will be monitored.*

*If concerns or problems are identified by the SMC, they will be reported to the IRB and NINR/NIH via email by [name] and [name], respectively, within 3 business days after they are identified. If there are recommendations made by the SMC, the action plan for response or notice of any actions taken by the IRB regarding the research and any responses to those actions will be provided to NINR Officials within 2 weeks.*

*e) Investigator compliance – Compliance of the investigators and all research team members who will have access to the data will be monitored annually. All research team members will be CREC certified; the CWRU intranet hosts a website where verification of compliance with continuing education for all investigators and team members can be evaluated.*

*2.) Reviewing and Reporting Adverse Events/unanticipated problems*

*a) Event identification- At the onset and for the duration of the study, all research staff and investigators will have instructional review of the nature and types of unanticipated and adverse events as described by the CWRU IRB. Potential risks for this study may include caregiver distress and breach of confidentiality (as described above). Caregiver distress may be identified by the data collector (during data collection) or the interventionist (during the interventions or phone follow-up). Breach of confidentiality may be identified by any research team member.*

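### The primary 4 x 3 RMANOVA in effect analyses only caregivers seen at all three waves, and the plan gives no method for missing waves

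*Combined protocol and SAP*

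**What the plan says.** **Analysis.** The Data Analysis Plan sets the method for aim A1: "The primary analysis will be a set of 4 group X 3 time waves RMANOVA". Its main stated safeguard is the sphericity check: "If the assumption of sphericity is violated based on the Mauchly's test, SPSS provides and adjusted F, df, and P-value in RMANOVA". The same section covers normality, influential cases and transformations for the other aims. It names no mixed model, imputation, missing-data assumption, analysis population or missing-data sensitivity analysis.

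**Data collection.** Study Design/Procedures states: "There are three structured data collection time points" (T1, T2 and T3). Under the COVID-19 modifications, a T2 or T3 session may count as missed if phone, video and emailed surveys all fail, and "if we cannot wait to collect the data in person at a later date".

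**Withdrawal.** Withdrawal of Research Participants treats unresponsive caregivers as lost to follow-up and stops data collection at withdrawal. It says that data from before "withdrawal will be de-identified and still be used in the data analysis for the study".

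**Monitoring.** Under Monitoring Study Safety, the committee reviews "missing data (including whether there are systematic patterns or whether data are missing at random". It also watches for differential attrition across the four groups. Neither review is tied to an analysis.

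**The concern.** The plan does not write down a completers-only rule. The rule follows from the named procedure, which needs all three waves from each caregiver for each outcome. Someone who misses T2 but attends T3, or who withdraws after T2, leaves A1 altogether.

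Three things are at stake.

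- **Precision and power.** T1 and T2 outcomes already collected are discarded.
- **Bias.** If dropout depends on the outcome differently in different arms, the completers' group effect and time x group contrast can be wrong in either direction. Nothing in the documents shows that this will happen, but the analysis has no defence if it does.
- **Consistency.** For A1, the promise to use data from before withdrawal cannot be kept with this method. The conflict is confined to A1. Baseline records can still serve the other aims; for example, "The supplemental analysis will use baseline data (T1").

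**Working it through.** **Inputs.** The documents give four arms, three waves and a target of 360. They give no alpha, power, effect size, SD, wave correlation or dropout rate, so the 360 cannot be reproduced. Assumed here: 90 per arm, SD 1, all wave correlations 0.6, alpha 0.05.

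**1. Who is left**

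- Completers = 360(1 - d). For d = 10, 20, 30, 40% this gives 324, 288, 252, 216.
- If instead 10% miss T2 and 10% miss T3 independently, completers = 360 x 0.9 x 0.9 = 292. Caregivers with T1 and at least one follow-up = 360 x (1 - 0.1 x 0.1) = 356.

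**2. Precision, random monotone loss** (half before T2, half before T3)

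For a contrast c with wave covariance S, the variance per randomised caregiver is:

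- completers: c'Sc / (1 - d)
- likelihood: c'I⁻¹c, where I = (d/2)I₁ + (d/2)I₂ + (1 - d)I₃ and I_k is the inverse covariance of the first k waves, padded with zeros.

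Worked case, d = 20%:

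- T3-T1: completers 2(1 - 0.6)/0.8 = 1.000; likelihood 0.9475; SE ratio √(1.000/0.9475) = 1.027.
- Three-wave mean: completers [(3 + 6 x 0.6)/9]/0.8 = 0.9167; likelihood 0.7635; SE ratio √(0.9167/0.7635) = 1.096.

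| SE ratio, completers/likelihood | 10% | 20% | 30% | 40% |
|---|---|---|---|---|
| T3-T1 | 1.013 | 1.027 | 1.042 | 1.059 |
| T3 | 1.021 | 1.044 | 1.068 | 1.095 |
| Three-wave mean | 1.044 | 1.096 | 1.157 | 1.230 |

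Over correlations 0.4-0.8 and 10-40% loss, the ranges are 1.010-1.075, 1.010-1.173 and 1.039-1.261.

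**3. Power** (25% random loss; 0.30 SD at T2 and T3 in both SM arms; 4,000 replicates)

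- Time x group: RMANOVA 65%, mixed model 73%.
- Group: RMANOVA 34%, mixed model 42%.

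**4. Type I error of the group test** (no true effect, about 25% loss, 4,000 replicates)

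Dropout model: logit P(drop before next wave) = a + b x previous score. Random loss: a = -1.87, b = 0. Score-related loss: a = -2.05, b = -0.7.

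| Loss pattern | RMANOVA | Mixed model |
|---|---|---|
| Random, equal | 5.0% | 4.8% |
| Random, 10% in one arm and 30% in three | 5.6% | 4.7% |
| Score-related, all arms alike | 4.8% | 5.0% |
| Score-related, control only | 12.3% | 5.2% |
| Score-related, both SM arms only | 15.1% | 5.2% |

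The RMANOVA time x group test stayed at 4.7-5.2% in these cases. That depends on the scenario. In a separate simulation (3,000 replicates, loss only after T2, slope 1 on the T2 score), time x group error was 8-9% when the dependence held in two arms and about 21% when it ran in opposite directions between arms.

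**5. Direction** (two arms, 6,000 replicates, 23-25% lost, b = -0.7 in one arm and random loss in the other)

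True T3-T1 effect = 0.30; true three-wave mean effect = (0 + 0.30 + 0.30)/3 = 0.20.

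| Score-related loss in | Completers T3-T1 | Completers mean | Likelihood T3-T1, mean |
|---|---|---|---|
| Control | 0.33 | 0.08 | 0.30, 0.20 |
| Intervention | 0.27 | 0.32 | 0.30, 0.20 |

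**6. Where the mixed model does worse.** With loss depending on the unseen score in one arm (b = -1, 20-25% lost), its T3-T1 was 0.38 or 0.22 against a true 0.30. Completers gave 0.34 or 0.26.

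**The case against.** - **The restriction is inferred, and missing waves are mentioned only conditionally.** Both points are true. The inference is still firm, because Mauchly's test and the adjusted F belong to the classical procedure. A method should be fixed in advance precisely because the amount of loss is unknown.
- **Differential attrition is monitored, and committee concerns must be reported and answered.** This is a real safeguard for trial conduct, but it does not say how an incomplete record enters A1.
- **The bias and power figures depend on chosen scenarios.** This stands. At b = -0.3 the group-test error is only about 6-7.5%. The inflated test is also the group main effect, which averages in the pre-randomisation wave, whereas the question about change over time rests on time x group. With a gradual effect (0.15 then 0.30 SD) and 25% loss, time x group power is 50% against 54%. With the flat effect and 10% loss it is 74% against 77%.
- **The mixed model is not always better.** This also stands. Under the unseen-score loss in step 6, its T3-T1 error was about 0.08 SD against 0.04 for completers. The proposal therefore needs a second sensitivity analysis.

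**Conclusion.** The concern holds. The named primary method in effect excludes every caregiver with a missing wave, the analysis plan offers no alternative, and for A1 this conflicts with the promise to use data collected before withdrawal. That conclusion rests on the documents and on how the procedure works, and confidence in it is high.

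The size of the harm cannot be fixed from the documents. Random loss, or loss related to scores in the same way in all arms, costs mainly precision: a few per cent in standard error for T3-T1, and more for the group mean. Material bias or false-positive inflation requires outcome-related dropout that differs between arms, and it grows with the strength of that dependence. The simulated figures are illustrations under the stated assumptions, not predictions. The point should be fixed, and the improvement is cheap.

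**What to change.** In the Data Analysis Plan:

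1. Make the primary A1 analysis a linear mixed model for repeated measures in SPSS MIXED, with arm, wave, arm x wave, unstructured covariance and REML. Include every randomised caregiver in the assigned arm with all observed waves. The planned group, time x group and linear and quadratic trend tests can all be taken from this model.
2. State that it assumes data are missing at random.
3. Keep the completers RMANOVA as a sensitivity analysis.
4. Add one sensitivity analysis for data not missing at random. For example, shift imputed T2 and T3 values by arm over a stated range and report where the conclusion changes.
5. Say that the committee's findings on missingness and differential attrition will be reported beside these results.

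The cost is a wording change and slightly more analysis work, with the same software and data and no extra participants. The primary result would then rely on the missing-at-random assumption, which item 4 tests.

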## **Objectives**

*The study has two aims: the primary aim (A1) is to examine differences across the four groups (control, usual care, SM-need, and SM-preference) on caregiver health (health risks and mental and physical health) over time. We hypothesize that the caregivers who receive a self-management intervention based on need (SM-need) or preference (SM-preference) will have better outcomes than those in the usual care or control groups. Secondary aims are to: A2) explore whether caregiver baseline need or preference for intervention (i.e. choice) is associated with: a) care recipient's symptoms; b) caregiver reactions; and c) caregiver involvement and A3) build caregiver profiles from demographic/contextual factors that are associated with their needs and preferences for the self-management interventions (A3).*

*We will also conduct a supplemental analysis to examine relationships among psychological stress responses (caregiver reactions and caregiving involvement), physiological stress responses (heart rate variability domains), and caregiver characteristics (race and gender) in caregivers of people with bipolar disorder. The major aims of the supplemental analysis (SA) are to: SA1) determine whether there are differences by caregiver characteristics (race and gender) on measures of psychological stress responses (caregiving involvement and caregiver reactions), SA2) determine whether there are differences by caregiver characteristics (race and gender) on measures of physiological stress responses (heart rate variability domains), SA3) examine associations among indicators of psychological stress responses (caregiver reactions and caregiving involvement) and physiological stress responses (heart rate variability domains), and SA4) explore relationships among time and frequency domains of heart rate variability.*

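### The primary aim tests at least three health domains in separate RMANOVAs, with no deciding outcome, success rule, alpha or multiplicity control, so its family-wise error is not controlled

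*Combined protocol and SAP*

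**What the plan says.** The Objectives section of the combined protocol and SAP sets A1 as a comparison of four groups on "caregiver health (health risks and mental and physical health) over time". The hypothesis is that caregivers in the two self-management arms "will have better outcomes than those in the usual care or control groups". It does not say whether one, some or all of the outcomes must be better.

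The Data Analysis Plan carries this into the analysis: "The primary analysis will be a set of 4 group X 3 time waves RMANOVA". The models compare the four groups "across three time waves of health risks and physical and mental health outcomes". Besides differences over time, each model "also assesses group differences and the interaction of time X group". Linear and quadratic trends are added, with the remark that "RMANOVA can determine if these trends in the mean are significant", but no significance level is given there or elsewhere.

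The section's template prompt reads "If applicable, provide a power analysis, and study/safety endpoints". The text beneath it has no power analysis and no endpoint list that ranks the outcomes. It also has no testing order, composite, multivariate or global test, or multiplicity adjustment. The List of Data to be Collected mentions questionnaires on health risks and health outcomes but does not give the number of scores per domain.

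**The concern.** Three unranked outcomes are jointly primary and each gets its own model. Nothing in the plan prevents A1 from being called supported on the strength of whichever one reaches significance. Nor does the plan say which test inside each model decides. With several chances to succeed and no adjustment, the primary conclusion need not carry the error rate that readers will attach to it.

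The trial's main message about caregiver health rests on A1. The gap concerns the number of outcomes, so it would remain even if each model were reduced to a single effect and a single arm contrast.

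**Working it through.** The plan states no alpha, power, effect size or family-wise error rate, so there is no figure of its own to reproduce. The check asks what error rate follows from the plan under explicit assumptions.

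**Inputs from the documents**
- Three outcome domains (Objectives; Data Analysis Plan).
- Four groups and three waves (Data Analysis Plan).
- Target sample 360 (Number of Research Participants).

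**Assumptions**
- Alpha 0.05 per test.
- One score per domain.
- Any one significant result counts as success.
- Equal allocation, 360/4 = 90 per arm (the ratio is not stated).
- Equal correlation r between every pair of outcomes, varied from 0 to 0.9.
- For the full simulation, a within-person correlation of 0.6 across waves and no true effect.

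**Step 1: one deciding test per outcome**
- Independent tests: 1 − 0.95³ = 14.3%.
- Upper bound under any dependence: 3 × 0.05 = 15%.

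**Step 2: correlated outcomes, and two effects per model**

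The group x time test has (4 − 1)(3 − 1) = 6 df and the group test has 3 df. The table gives the chance of at least one rejection under the null, from 400,000 draws of correlated chi-square statistics.

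| r | group x time only (3 tests) | group or group x time (6 tests) |
|---|---|---|
| 0 | 14.3% | 26.4% |
| 0.3 | 13.8% | 25.5% |
| 0.5 | 13.0% | 24.2% |
| 0.7 | 11.4% | 21.4% |
| 0.8 | 10.3% | 19.4% |
| 0.9 | 8.7% | 16.6% |

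The closed form for six independent tests is 1 − 0.95⁶ = 26.5%. A full null simulation of the RMANOVA (6,000 replicates) agrees within simulation error. For group x time alone it gives 14.6% at r = 0, 11.9% at r = 0.7 and 10.6% at r = 0.8. For either effect it gives 26.8% at r = 0 and 21.5% at r = 0.7.

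**Step 3: sensitivity to the assumptions**
- Five scores across the three domains, independent: 1 − 0.95⁵ = 22.6%.
- Alpha 0.01 per test, three independent tests: 1 − 0.99³ = 3.0%.
- All three outcomes required to be significant: at most 5%.

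**Step 4: direction**

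The omnibus F test is non-directional. Under the null with equal arms, every ranking of the four arms is equally likely given a rejection.
- Both self-management arms rank above both comparators in 2! × 2!/4! = 1/6 of rejections. For three independent outcomes this gives 1 − (1 − 0.05/6)³ = 2.5%, against 0.05/6 = 0.8% for one outcome.
- If a self-management arm need only rank top, the share is 1/2 and the figure is 1 − (1 − 0.025)³ = 7.3%, against 2.5% for one outcome.

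Either way, three outcomes roughly triple the single-outcome rate.

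**Step 5: effect of a correction**

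At 0.05/3 = 1.67% per test, three independent tests give 1 − (1 − 0.05/3)³ = 4.9%, and at most 5% under any dependence. Holm has the same 5% bound.

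**The case against.** The strongest reply is that the plan never claims 5% and never says that any one outcome suffices. A reader might infer that the primary aim has a false-positive rate of 11–15% instead of a promised 5%. The documents do not support that as a fact. No alpha appears, the success rule is undefined, the number of scores is unknown, and the correlations are not given. A stricter alpha, or a rule that all outcomes must be positive, would bring the rate to 5% or below. This part of the reply stands, and the figures are conditional for that reason.

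A reader might also take 11–14% as the chance of wrongly announcing that self-management works. That does not follow either. The figure counts any false difference among four groups, including those in which a comparator arm does best. By the rankings in Step 4, a false favourable claim is rarer.

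Nor do the documents show an intention to pick an outcome after seeing the data, since all three domains are declared in advance. The plan leaves room for such a choice but does not describe one.

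None of this closes the gap. The plan contains no all-must-pass rule, stricter alpha or adjustment that would hold the error down, and these omissions are the defect. The conditional figure could also be too low, because the plan describes group, interaction and trend tests in each model without saying which decides.

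**Conclusion.** The concern holds in conditional form. A1 has at least three co-primary health domains, each tested in its own RMANOVA, and the documents give no deciding outcome, success rule, alpha or multiplicity control. With one test per domain at an assumed 5% and any one result counting, the chance of at least one false group x time difference is about 11–14% for outcome correlations of 0 to 0.7, and never above 15%. Counting either the group or the group x time effect raises it to about 21–26% over the same range. It falls to roughly 9–10% at correlations of 0.8 to 0.9. It would be at most 5% if all three outcomes had to be significant, which the plan does not require.

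The issue affects how the primary result can be interpreted and should be settled before the arms are compared. It does not undermine the conduct of the trial.

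**What to change.** Before any arm-level data are examined, amend the Data Analysis Plan, and the Objectives to match, as follows.

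1. State alpha.
2. Name one measure for each of the three domains.
3. Name one deciding effect or contrast per RMANOVA, for example group x time. Neither option below can hold the error at 5% without this, because the plan currently describes several tests per model.
4. Then choose one option:
   - name one of the three measures as the A1 primary outcome and make the other two secondary; or
   - keep all three and apply Holm to the three deciding p-values (ordered thresholds 1.67%, 2.5% and 5% if alpha is 5%), claiming benefit only for outcomes that pass. If the deciding effect is an omnibus test, a pass shows only that the groups differ, so the direction must be checked as well.

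The cost is one or two sentences and no new data. Naming one outcome costs that outcome no power. Holm costs some. As an illustration only, take a two-arm t-test with 90 analysed per arm and a standardised difference of 0.42. Power is 80% at 5%, about 71% at 2.5% and about 66% at 1.67%. This is not the planned interaction test, and it assumes equal allocation and no missing data.
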